## 9. INDIVIDUAL DATA LISTINGS

All data collected in the eCRF will be listed. Individual data listings will be provided in an excel file, with one tab for each form. In addition, analysis sets, and randomization arm of each patient will be added in each tab. MedDRA and WHO-Drug coding will be listed in the corresponding tabs.

## 10. CHANGES IN THE STATISTICAL METHODS FROM THOSE STATED IN THE PROTOCOL

This SAP is based on protocol version 2.0 and CRF version 2.0.

Changes in the statistical methods compared with those stated in the protocol are the following.

Add analysis subgroups:

- Subgroups analysis (“NPC > 5 at D0 before treatment”, “Horizontal deviation at D0 before treatment”, “Vertical deviation at D0 before treatment” (Maddox rod vertical – Left eye) and “Vertical deviation on at least one eye at D0 before treatment” (Maddox rod vertical – Both eyes), “number of previous concussions”).

Add secondary endpoints:

- Rombert quotient and Statokinetic distribution index calculation.

Add analysis of:

- NPC measurement in the subgroup “NPC > 5 at D0 before treatment”.
- Maddox rod horizontal score in the subgroup “Horizontal deviation at D0 before treatment”.
- Maddox rod vertical left eye in the subgroup “Vertical deviation at D0 before treatment”
- Maddox rod vertical both eyes in the subgroup “Vertical deviation at least one eye at D0 before treatment”.

Add descriptive analysis of ADE occurring during the first session (D0) and during the second session (at D7).

Add Exploratory analyses: study of potential relationship between drowsiness and concussion severity parameters.

There were no other changes in the statistical methods from those stated in the protocol.

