9.6. Statistical Considerations

9.6.1. Sample Size Justification

For a sample size of 50 patients, the probability of observing at least one ADE will be 0.87 considering a probability of ADE of 0.04. The sample size calculation was performed with SAS® v9.4.

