9.6.3. Statistical Analysis

Full details related to statistical analysis will be provided in the Statistical Analysis Plan.

The statistical analysis will be performed using SAS® Viya v9.4 (or a more recent version).

The global significance level (type I error rate) will be set at $\alpha = 0.05$ (two-sided). Adjustment for multiplicity is not applicable for the primary endpoint and no adjustment for multiplicity is planned for secondary endpoints.

Continuous data will be described by the number of missing data, number of data analyzed, mean, standard deviation, median, Q1, Q3, minimum, maximum.

Categorical data will be described by the number of missing data, frequencies and percentages of patients in each modality. The percentage of patients will be calculated once missing data are excluded from the denominator.

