9.6.3.2. Secondary Endpoints Analysis

ADEs per severity

A descriptive analysis with 95% exact Clopper-Pearson confidence interval of mild, moderate and severe ADEs will be provided in the FAS, by treatment groups and overall.

AEs

All AEs will be described in the FAS, for each System Organ Class (SOC) and Preferred Term (PT) class using MedDRA (Medical Dictionary for Regulatory Activities) terminology, by treatment groups and overall.

DDs

All DDs will be described in the FAS, by treatment groups and overall.

| | |
|--|--------------|
| 2022.08.11_RGnCON_Prot_Final_V2.0_clean_public | Page 48 / 82 |
|--|--------------|

Secondary performance analyses

The secondary performance analyses will be performed in the FAS by treatment groups, excluding data that would be collected after the following intercurrent event: treatment group switch during follow-up.

Imputation of missing data will be handled by the mixed model (details will be provided in the Statistical Analysis Plan).

The analyses will be performed as follows:

- For the evolution of the below parameters, the following timepoints will be compared: (D0 after treatment - D0 before treatment, D7 before treatment - D0 before treatment, D7 after treatment - D0 before treatment, and D52 – D0 before treatment) and a mixed effect regression model will be used with a patient random effect. Group effects (5 Hz vs 10Hz), period effects (D0 before, D0 after, D7 before, D7 after and D52) and the group-by-period interaction will be added as fixed effects. The stratification variables will be added in the model as covariates.
 - Automated oculomotor and oculopostural functions:
 - Convergence, evaluated with the Near Point of Convergence (NPC) (>5 cm vs ≤5 cm)
 - Deviation as evaluated with the cover test (normal fixation or light restitution movement or important restitution movement or deviated eye without restitution movement)
 - Horizontal deviation as evaluated with the Maddox rod test (orthophoria or exophoria or esophoria and measure in diopter)
 - Vertical deviation of the right eye as evaluated with the Maddox rod test (orthophoria or hypophoria or hyperphoria and measure in diopter)
 - Vertical deviation of the left eye as evaluated with the Maddox rod test (orthophoria or hypophoria or hyperphoria and measure in diopter)
 - Balance function:
 - Statokinesigram area (m²)
 - Difference between left distribution and right distribution (%)

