## 2. VERSION HISTORY

Version	Date	Author	Comment / changes
0.1	25/10/2022	[REDACTED]	Initial draft version (based on protocol version 2.0, dated 11/08/2022)
0.2	08/03/2023	[REDACTED]	Comments from RGnCON
1.0	05/05/2023	[REDACTED]	First approved and signed version (based on protocol version 2.0, dated 11/08/2022)
1.1	31/07/2023	[REDACTED]	Draft version after data review
2.0	03/08/2023	[REDACTED]	Second approved and signed version (based on protocol version 2.0, dated 11/08/2022)

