#### 6.2.2. Secondary performance endpoints

According to section 9.5.4.2 of the Protocol, the following endpoints will be used to address Secondary performance objectives:

- Automated oculomotor and oculopostural functions will be used as recorded in the eCRF, before and after treatment session at D0 and D7 and then at D52:
  - Convergence, evaluated with the measure of the Near Point of Convergence (NPC)
  - Deviations:
    - Cover test
      - Normal fixation of both eyes
      - Abnormal with at least one eye
    - Maddox rod test:
      - Horizontal deviation (yes/no)
      - Vertical deviation right eye (yes/no)
      - Vertical deviation left eye (yes/no)
- Balance function will be used as recorded in the eCRF, before and after treatment session at D0 and D7 and then at D52:
  - Patient's eyes opened

- Statokinesigram area (mm^2)
- Left distribution (%)
- Right distribution (%)
- Patient's eyes closed
  - Statokinesigram area (mm^2)
  - Left distribution (%)
  - Right distribution (%)
- Rombert quotient (RQ)

The Romberg quotient is the ratio between the statokinesigram area (mm^2) with closed eyes (CE) and the statokinesigram area (mm^2) with opened eyes (OE), it will be calculated as follow :

$$RQ = CE/OE.$$

- Statokinetic distribution index (SKDI)

The stato-kinetic distribution index (SKDI) is the result of the STKG area multiply by the ratio of support distribution it will be calculated as follow:

$$SKDI (\text{mm}^2) = STKG \text{ area } (\text{mm}^2) \times (D/d^*)$$

\*D : Highest distribution value (%)

d : Lowest distribution value (%)

- TMT A&B before treatment session at D0 and after treatment session at D7:
  - TMT – A
    - Time to perform the task will be derived as:  
$$\text{Time to perform the task (in second)} = \text{minutes} * 60 + \text{second.}$$
    - Number of errors (will be used as recorded in the eCRF)
  - TMT –B
    - Time to perform the task will be derived as:  
$$\text{Time to perform the task (in second)} = \text{minutes} * 60 + \text{second.}$$
    - Number of errors (will be used as recorded in the eCRF)
  - TMT – B - A
    - Time to perform the task will be derived as:  
$$\text{Time to perform the task (in second)} = \text{Time to perform the task B} - \text{Time to perform the task A}$$
    - Number of errors will be derived as:  
$$\text{Number of errors} = \text{Number of errors B} - \text{Number of errors A}$$

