#### 8.5.1.1. Automated oculomotor and oculopostural functions and balance function

For the evolution of parameters of oculomotor and oculopostural functions and balance function defined in Section 0, the following timepoints will be compared: (D0 after treatment - D0 before treatment, D7 before treatment - D0 before treatment, D7 after treatment - D0 before treatment, and D52 – D0 before treatment). A mixed effect regression model (logistic model for a categorical parameters and a linear model for continuous parameters) will be used with a patient random effect. Group effects (5 Hz vs 10Hz), period effects (D0 before, D0 after, D7 before, D7 after and D52) and the group-by-period interaction will be added as fixed effects. The stratification variable gender (male/female) will be added in the model as covariates.

Note: the stratification variable concussion history within 6 months prior to inclusion (yes/no) will not be added in the model as too few patients had concussion history (cf. data review minutes of 18/07/2023).

The following template will be used for continuous parameters.

	Group of treatment		
Ref = D0 before treatment	RGn550 5Hz N=xx	RGn550 10Hz N=xx	Difference
Endpoint XXX at D0 after treatment			
Adjusted mean	x.xx	x.xx	x.xx
95% CI	x.xx ; x.xx	x.xx ; x.xx	x.xx ; x.xx
p-value	.	.	0.xxx
Endpoint XXX at D7 before treatment			
Adjusted mean	x.xx	x.xx	x.xx
95% CI	x.xx ; x.xx	x.xx ; x.xx	x.xx ; x.xx
p-value	.	.	0.xxx
Endpoint XXX at D7 after treatment			
Adjusted mean	x.xx	x.xx	x.xx
95% CI	x.xx ; x.xx	x.xx ; x.xx	x.xx ; x.xx
p-value	.	.	0.xxx
Endpoint XXX at D52			

		Group of treatment		
Ref = D0 before treatment		RGn550 5Hz N=xx	RGn550 10Hz N=xx	Difference
Adjusted mean		x.xx	x.xx	x.xx
95% CI		x.xx ; x.xx	x.xx ; x.xx	x.xx ; x.xx
p-value		.	.	0.xxx

From an mixed model including treatment (p=0.xxx), visit (p=0.xxx), treatment-by-visit interaction (p=0.xxxx) as fixed effects and variable xxx as random effect, variableyyy (p=0.xxx) as baseline covariate.

The following template will be used for categorical parameters.

	RGn550 10Hz vs RGn550 5Hz at visit 1	RGn550 10Hz vs RGn550 5Hz at visit 2	visit 2 vs visit 1 at RGn550 10Hz	visit 2 vs visit 1 at RGn550 5Hz
Endpoint XXX				
Odds ratio	X.X	X.X	X.X	X.X
95% CI	[X.X ; X.X]	[X.X ; X.X]	[X.X ; X.X]	[X.X ; X.X]

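### SAP Section 10 says nothing else changed from the protocol, but its list omits six changes to secondary endpoints and models, including the unexplained move of Maddox from dioptres to yes/no

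*SAP*

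**What the plan says.** Section 10 of the SAP declares added subgroups, two added balance indices (Romberg quotient and SKDI), subgroup analyses, adverse device effects (ADEs) by session and a drowsiness analysis. It then states "There were no other changes in the statistical methods from those stated in the protocol".

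Protocol 9.6.3.2 defines the horizontal Maddox endpoint as "Horizontal deviation as evaluated with the Maddox rod test (orthophoria or exophoria or esophoria and measure in diopter", and treats vertical deviation of each eye in the same way. SAP 6.2.2 makes all three binary, for example "Vertical deviation right eye (yes/no". It reduces the cover test to normal in both eyes against "Abnormal with at least one eye".

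On covariates, SAP 8.5.1.1 says that concussion history "will not be added in the model as too few patients had concussion history" and cites data review minutes of 18/07/2023. The version history labels v1.1 "Draft version after data review".

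**The concern.** A change section exists so that a reader can separate what was fixed in the protocol from what was decided later. A reader who trusts the closing sentence would take the SAP's Maddox, cover test and balance outcomes, and its model covariates, as the protocol's own.

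Two features make this more than tidiness. The secondary endpoints carry no multiplicity adjustment, so the main protection against selective choice is a clear record of what was planned. The current SAP was also signed after the data had been reviewed, in a trial where only patients are blinded. Separately, the binary Maddox definition does not work in the subgroups that the SAP itself adds.

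**Working it through.** **1. The plan's only design figure.** Protocol 9.6.1: "For a sample size of 50 patients, the probability of observing at least one ADE will be 0.87 considering a probability of ADE of 0.04". Check: 1 − 0.96^50 = 1 − 0.1299 = 0.8701, so 0.87 is reproduced. No effect size, SD or power is given for any performance endpoint, so the changes below contradict no stated power. On testing, Protocol 9.6.3 says "The global significance level (type I error rate) will be set at" 0.05 two-sided, without adjustment for secondary endpoints.

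**2. Side-by-side comparison.**

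| Item | Protocol | SAP | In Section 10? |
|---|---|---|---|
| Maddox (horizontal, right vertical, left vertical) | Three-level direction plus dioptres (9.6.3.2) | Yes/no (6.2.2); no dioptre variable defined | No |
| Cover test | Four grades (9.5.5.1, 9.6.3.2) | Two categories, eyes combined (6.2.2) | No |
| Stabilometry | Mean of the eyes-open and eyes-closed records (9.5.5.1); left-right difference (9.6.3.2) | Eyes open and closed separately; left and right separately (6.2.2) | No |
| Concussion history covariate | In all mixed models (9.6.3.2) | Removed with a reason in 8.5.1.1; absent without comment for TMT (8.5.1.2); SCAT5 text still refers to the stratification variables in the plural (8.5.1.3) | No |
| SCAT5 baseline covariate | Not included (9.6.3.2) | Added (8.5.1.3) | No |
| Pooled D0–D52 model, all patients | Not included | Added in the note after 8.5.1.3 | No |

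Section 10 does list other added analyses, so by its own practice the pooled model belongs there.

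On the stabilometry row, if the two percentages sum to 100 (an assumption, though implied by their description), L − R = 2L − 100. Left, right and signed difference then carry the same information. The substantive change is analysing eyes open and eyes closed apart instead of their mean.

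**3. NPC.** Protocol 9.5.4.2 names the measured distance; Protocol 9.6.3.2 names the 5 cm cut. SAP 6.2.2 follows 9.5.4.2 and keeps the cut only to define a subgroup. The protocol is inconsistent here, so this is a choice to state, not an undeclared departure.

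**4. Dates.** SAP v0.1 25/10/2022; v1.0 05/05/2023; data review minutes 18/07/2023; v1.1 31/07/2023; v2.0 03/08/2023. From 18 July to 3 August is 16 days. The SAP ties three statements to a data review: removal of the history covariate and omission of the right-eye Maddox subgroup (both 8.5.1.1), and the 0% loss to follow-up (8.4.1).

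**5. Maddox in its own subgroups.** SAP 8.5.1.1 analyses horizontal deviation among patients with horizontal deviation at D0. If n patients are in the subgroup, D0 has n yes and 0 no, so the D0 odds are n/0. An odds ratio of any later visit against D0 therefore has no finite, non-zero estimate, whatever happens later. The left-eye vertical subgroup has the same problem. So does the both-eyes subgroup if its outcome is deviation in at least one eye, but 6.2.2 does not define that outcome. Section 10 mentions a horizontal Maddox score that is likewise never defined.

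**6. Two model statements that do not work as written.** In the SCAT5 model D0 is a modelled timepoint and baseline SCAT5 is a covariate. At D0 the response equals the covariate, so its slope there is exactly 1 with no residual, while a single slope is fitted over all visits. The pooled model includes TMT, which Protocol Table 2 and SAP 6.2.2 place only at D0 before treatment and D7 after treatment, so there is no D52 value to model.

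**The case against.** The protocol leaves full statistical detail to the SAP, and the model core is unchanged: patient random effect, group, period and interaction all remain. Choosing logistic or linear forms is legitimate specification. The history covariate's removal is disclosed with its reason in 8.5.1.1, and Romberg quotient and SKDI are declared in Section 10. All of this stands: the models were modified, not replaced, and those two indices do not contradict the closing sentence. Leaving detail to the SAP does not, however, cover a changed endpoint definition under a statement that nothing else changed.

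A reader might infer two stronger things, and the documents support neither.

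- *That the review was unblinded and drove the endpoint changes.* The SAP does not say whether treatment groups were visible. Patient-only blinding makes that possible but does not show it. Versions 0.1 to 1.0 are not available, so the Maddox, cover test and stabilometry definitions, Romberg quotient and SKDI cannot be placed before or after the review.
- *That yes/no Maddox costs a known share of the sample.* For a normal variable cut to leave 10% to 50% on one side, the retained information φ(c)²/(p(1 − p)) is 0.342 to 0.637, or 8.6 to 15.9 of 25 patients per arm. Dioptres are not of that shape: prisms are used only when a deviation is found (Protocol 9.5.5.1), so orthophoria forms a mass at zero, and deviations run in two directions. Suppose treatment changes only the proportion p with a deviation, whose size has coefficient of variation CV. The efficiency of yes/no relative to dioptres is then (CV² + 1 − p)/(1 − p) = 1 + CV²/(1 − p). At assumed CV 0.5 and p 0.3 this is 1 + 0.25/0.7 = 1.36, favouring yes/no. The loss or gain depends on facts not in the documents.

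Dioptres may also be intended in the subgroup analyses, given the undefined score, and all eCRF data are to be listed. The supportable claim is that the dioptre analysis is missing from the endpoint definitions, not that the data are lost.

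**Conclusion.** The concern holds as an incomplete change list. Six differences from the protocol are absent from Section 10, and NPC needs a stated choice. The covariate item is enough on its own to contradict the closing sentence, because the SAP documents that change in 8.5.1.1 and cites the review for it.

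The yes/no Maddox outcome cannot give change from D0 as an odds ratio in subgroups selected for deviation at D0. The pooled TMT analysis cannot be run. The SCAT5 covariate text needs correcting. None of these three conclusions depends on a numerical assumption.

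No figure is put on lost precision, and no claim is made that changes were chosen with knowledge of results by arm. The effect is confined to secondary performance endpoints of a pilot. The primary analysis, the proportion with at least one ADE with its Clopper-Pearson interval, is the same in both documents.

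**What to change.** - Delete the closing sentence of Section 10. List all six changes and the NPC choice, each with its reason, its date relative to 18/07/2023 and whether allocation was visible when it was made. Give the same dates for Romberg quotient and SKDI.
- Label as post hoc exploratory only those analyses shown to have been first introduced after the review.
- Analyse the protocol's Maddox dioptre measure for horizontal, right vertical and left vertical deviation, and in the deviation subgroups, with yes/no as supplementary. State whether values are signed or absolute, since opposite directions can cancel when signed. Report descriptively where deviations are too few to model; the SAP already reports too few for the right-eye subgroup.
- Define or remove the horizontal Maddox score and the both-eyes outcome.
- Correct the TMT timepoint in the pooled model. In the SCAT5 text, say which stratification variables are used, and either drop the baseline covariate or remove D0 from the responses.

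The cost is SAP wording and up to three further linear models with their subgroup versions. This assumes that the prism values required by Protocol 9.5.5.1 were entered in the eCRF. If the analysis has already been run, the same list and labels belong in the clinical investigation report.

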## 11. QUALITY CONTROL

A self-validation will be performed by the statistician in charge of the analysis as follows: each derived variable will be validated exhaustively (i.e. on all patients) whenever possible. Exhaustive controls can be performed using either contingency tables (i.e. displaying all qualitative variables and minimum/maximum values of quantitative variables involved in the derivation rules) or individual data listings that are considered as not too large (i.e. no more than 50 rows). An exhaustive control is considered possible when the corresponding output contains up to 50 rows. For validation outputs considered as too large (i.e. more than 50 rows), the validation can be performed on a minimum of 5% patients randomly drawn. If the validation output is still too large (i.e. more than 50 rows), the validation will be performed on a subset of 50 rows (minimum).

Validation outputs will be reviewed by a third party (i.e. head of biostatistics or another statistician).

Derivation of the primary endpoint will be double-checked by a third party (i.e. head of biostatistics or another statistician).
